3 STUDY DESIGN

This is an evaluation of an ongoing national screening programme. In years 1 and 2, we will implement an enhanced metrics and evaluation project at selected sites in all provinces across South Africa to measure 6-month outcomes of this programme, along with operational challenges. In years 2 to 5 we will implement programmatic strategies to maximize 6-month cryptococcal meningitis-free survival.

Per South African standard of care, those with a CD4<100 cells/µL will reflexively get a CRAG test performed on remaining blood specimen. We expect the majority of these persons to be asymptomatic outpatients presenting for routine HIV care, though a small proportion will be persons who present to care because they feel unwell. All participants will receive standard of care treatment for asymptomatic cryptococcal antigenaemia, per South African HIV guidelines.

Primary Objective (years 1 and 2): To implement enhanced surveillance at selected sites to determine the outcomes (overall and for pre-specified subgroups) of a national reflex laboratory CRAG screening and pre-emptive treatment programme in South Africa. We estimate performing enhanced surveillance at **approximately 400 clinics out of 4500 clinics nationally**. A list of surveillance facilities will be agreed upon in discussion with provincial departments of health.

We will assess the cascade of care from CD4 testing to CRAG testing, to receipt of CRAG results by healthcare provider, assessment for symptoms, lumbar puncture if indicated, preemptive treatment for those asymptomatic, and 6-month outcomes.

The initial surveillance performed in Objective 1 will establish **baseline 6-month CRAG+ outcomes** (Year 1 and 2) from which subsequent programmatic interventions will seek to improve.

Subgroup Analyses

A number of subgroup analyses will be performed to understand optimal CRAG screening and treatment programmes. For example, we will compare outcomes amongst CRAG+ persons who:

- a) initiated on ART before CD4/ CRAG results are known (same-day ART initiation in the context of universal HIV test-and-treat) to those who have ART delayed until a minimum of 2 weeks of antifungal treatment completion
- b) rural clinics vs. urban centres
- c) high titres (\geq 160) vs. low titres (<160)

- d) clinics that routinely perform lumbar punctures to those that are unable to perform lumbar punctures (stratified by titre)

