- e) development of culture-positive cryptococcal meningitis. These lab results will be captured by the NHLS database, and additional queries by NICD personnel of medical records of CSF CRAG+ persons will be performed for secondary data review and quality assurance on the rate of capture of meningitis episodes. The GERMS surveillance system run by NICD will continue to capture cryptococcal meningitis among those lost to follow up or who transfer care.
- f) Cryptococcal meningitis-free survival of those who receive secondary prophylaxis vs. none
- g) Special populations: pregnant women, those with liver disease.

Such information will be particularly nuanced to the South African CRAG screening and treatment programme, but will also be informative to other sites in sub Saharan Africa that are initiating similar national programmes.

Active enhanced surveillance

Data will be collected by two methods:

A) primary (retrospective) data collection by chart/ record review at facility level by partners and B) secondary analysis and triangulation of existing laboratory and surveillance datasets.

Primary data collection by partners

We will collaborate with partners in South Africa to conduct active surveillance of all CRAG+ persons at selected facilities using a standardized data collection tool (attached – version 1.0, 4 January 2017). Please see appendix for list of partners, and potential roles. Partners may assist with monitoring and evaluation, capturing health information, contact tracing of those who are lost-to-follow up, and/or collecting operational information.

Partners will review patient demographics and outcomes of those who are CRAG+ by retrospective chart/ record review. This will be performed approximately 3 times over a 6-month period, to obtain information about CRAG result, CD4 result, presence of CNS symptoms, receipt of fluconazole if appropriate, and triage to lumbar puncture if symptomatic, along with timing of ART initiation, 6-month survival, retention-in-care, and incidence of cryptococcal meningitis.

Surveillance will not occur at all facilities across South Africa, but at selected facilities within each South African province. A list of surveillance facilities will be agreed upon in discussion with provincial departments of health.

Secondary analysis and triangulation of existing datasets noted on pages 13 and 14.

- Cohort of those with advanced HIV (CD4 <100), incl. CRAG results
 - Subset of those with a positive CRAG result

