Probabilistic sensitivity analysis will be performed thereafter to account for uncertainty in parameter such as loss to follow up, or performance of lumbar punctures –which will likely vary by site. This will yield more nuanced data regarding the efficiency of CRAG screening programs, and important barriers to overcome for comprehensive, cost-effective care.

2. Evaluate risk factors for treatment failure.

The purpose of this objective is to define high-risk populations that may require customized, intensive care in the future. We hypothesize that high initial CRAG titres in blood (≥160), is a risk factors for meningitis and death. Preliminary data from the original ORCAS study in Uganda from 2012 to 2014 suggests that CRAG titre is a risk factor for death.

Other risk factors may include rapid or same-day ART initiation, delay in ART initiation >2 weeks from initial CD4 blood draw, delays in initiation of fluconazole beyond 2 weeks from initial CD4 blood draw, stock outs of fluconazole, etc.

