8.1 Statistical Analysis Plan

The rate (with 95% confidence interval) for the primary and secondary events will be estimated overall and for pre-specified subgroups during the first 2 years of the study. Those rates will subsequently be compared with the rates after programmatic changes have been made (during years 2-5) to increase the effectiveness of the national screening program.

For the subgroups we will also use time-to-event methods to compare the primary and selected secondary endpoints. The table below reports detectable hazard ratios for the primary event with 80% and 90% power, assuming a two-sided alpha=0.05, 70% CM-free survival in the control group, and the stated number of subgroup participants. For example, if CSF CRAG titre data are available for 1200 participants (with 300 having a titre \geq 160), then we can detect a hazard ratio as small as 1.37, for an almost 10% difference in event-free survival.

Detectable Hazard Ratios for Subgroups					
(Assuming two-sided α =0.05 and 70% event-free survival in the control group)					
		80% Power		90% Power	
	N per		Proportion		Proportion
Subgroup	group	HR	Surviving	HR	Surviving
High CSF CRAG titre	300	1.37	0.61	1.44	0.60
(≥1:160)					
Control	900				
(CSF CRAG titre < 1:160)					

The a priori subgroups of interest are:

- High CRAG titres (\geq 1:160) vs. low titres (<1:160)
- Male vs. Female
- Pregnant vs. Non-pregnant
- Liver Disease (ALT>3x Upper Limit of Normal) vs. No liver disease

- Geographic Location (urban vs. rural)
- Timing of ART Initiation
 - On pre-existing ART
 - Initiated on ART before CD4/ CRAG results are known (same-day ART initiation in the context of universal HIV test-and-treat)
 - ART initiated at 2 weeks
 - ART initiated at >=4 weeks
- Clinic-level outcomes (i.e. cluster) based on proportion of CRAG+ persons receiving Lumbar Punctures.
- Duration of fluconazole use
- Fluconazole secondary prophylaxis vs. none

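### Several a priori subgroups in Section 8.1 are defined by treatment after the CRAG+ result, and no time origin, landmark or time-updated exposure is set for comparing them

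*Protocol*

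**What the plan says.** The primary endpoint is 6-month cryptococcal meningitis-free survival among people with a CRAG+ result. Death from any cause and symptomatic meningitis both count as failures (Protocol Summary; Section 8, Primary Endpoint).

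Section 8.1 states: "For the subgroups we will also use time-to-event methods to compare the primary and selected secondary endpoints". The a priori list that follows mixes two kinds of subgroup:

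- **Fixed at or near the CRAG+ result:** titre, sex, pregnancy, liver disease, location, pre-existing ART, and ART begun before results are known.
- **Known only later:** ART at 2 weeks, "ART initiated at >=4 weeks", duration of fluconazole use, and "Fluconazole secondary prophylaxis vs. none".

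Section 3 (Subgroup Analyses) repeats two of the later contrasts. Item (a) sets same-day ART against "ART delayed until a minimum of 2 weeks of antifungal treatment completion". Item (f) is "Cryptococcal meningitis-free survival of those who receive secondary prophylaxis vs. none". Item (e) in the same list is "development of culture-positive cryptococcal meningitis". Among possible risk factors for treatment failure, Section 3 also names "delay in ART initiation >2 weeks from initial CD4 blood draw".

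The only power calculation, in Section 8.1, is for the titre contrast, "assuming a two-sided alpha=0.05, 70% CM-free survival in the control group".

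**The concern.** To be counted as starting ART at 4 weeks or later, or as receiving secondary prophylaxis, a patient must first reach that date without dying or developing meningitis. Patients who fail earlier cannot be in the group. In the prophylaxis contrast they land in the none group. In the ART-timing contrast they land in no listed category, while the same-day group keeps all its early failures. Duration of fluconazole has the same structure, because failing early cuts the duration short. If the clock runs from CRAG+, the later-treated group is credited with a stretch of guaranteed event-free time.

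The stake is a false finding on questions the protocol itself treats as open. Section 1.1 lists the effect of same-day ART in advanced HIV as a knowledge gap. Section 3 says the subgroup analyses are meant to clarify what an optimal screening and treatment programme looks like. It also stratifies costs and effectiveness by secondary prophylaxis, so a biased contrast would carry into the cost-effectiveness results.

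**Working it through.** **Inputs from the protocol.** 70% event-free at 6 months, two-sided alpha 0.05, 300 versus 900 patients, detectable hazard ratio (HR) 1.37 at 80% power and 1.44 at 90% (Section 8.1). The WHO schedule described in Section 1.1 has phases of 2 and 8 weeks, so its third phase begins at week 10.

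**Assumptions.** The third phase is read as secondary prophylaxis. Half of patients are intended for each group. ART at 4 weeks or later is spread evenly over weeks 4 to 8. The hazard is constant, or front-loaded (Weibull shape 0.6 or 0.7). The exposure has no true effect. Six months is 26 weeks, and follow-up runs from CRAG+.

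**1. The plan's own figure.** Exposed survival at HR 1.37 is 0.7^1.37 = 0.61. Expected events are 300 × 0.3865 = 116 and 900 × 0.30 = 270. The standard error of log HR is √(1/116 + 1/270) = 0.111. Then ln(1.37)/0.111 − 1.96 = 0.88, which is 80.9% power. At HR 1.44 the same steps give survival 0.60 and 91.4% power. The table is reproduced. The plan's smallest detectable effect is therefore HR 1.37, or 0.73 in the protective direction.

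**2. Prophylaxis versus none, by hand, constant hazard.**
- Weekly hazard: −ln(0.7)/26 = 0.01372.
- Event-free at week 10: 0.7^(10/26) = 0.872.
- Event-free at 6 months, prophylaxis group: 0.70/0.872 = 80%.
- Event-free at 6 months, none group: 0.5 × 0.70/(1 − 0.5 × 0.872) = 0.350/0.564 = 62%.
- Prophylaxis group rate: 0.197 events per person over 10 + 0.197/0.01372 = 24.4 weeks, or 0.0081 per week.
- Total person-time is 0.30/0.01372 = 21.87 weeks per patient. The none group therefore has (21.87 − 0.436 × 24.37)/0.564 = 19.9 weeks each, with 0.380 events, or 0.0190 per week.
- Rate ratio: 0.0081/0.0190 = 0.42.

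**3. ART timing, by hand, constant hazard.**
- Start at week 6 (the middle of weeks 4 to 8): event-free to week 6 is 0.7^(6/26) = 0.921, and at 6 months 0.70/0.921 = 76%. The rate is 0.240/(6 + 0.240/0.01372) = 0.0102. Against the same-day rate of 0.01372 the ratio is 0.74.
- Start at week 2: event-free at 6 months is 0.70/0.973 = 72%. The rate is 0.2805/(2 + 0.2805/0.01372) = 0.0125, and the ratio is 0.91.

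**4. Cox simulation, no true effect** (front-loaded shape 0.6; false-positive rates at N = 1,200, 200 replicates):

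| Contrast, clock from CRAG+ | HR, constant hazard | HR, front-loaded | False positives |
|---|---|---|---|
| Prophylaxis vs none | 0.41 | 0.28 | 100% / 100% |
| ART ≥4 weeks vs same-day | 0.74 | 0.53 | 80% / 100% |
| ART ≥4 weeks vs 2 weeks | 0.82 | 0.76 | 44% / 69% |
| ART 2 weeks vs same-day | 0.91 | 0.76 | 17% / 70% |

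With the milder shape 0.7, prophylaxis gives about 0.31 and ART at 4 weeks or later about 0.6. For fluconazole duration the protocol gives no cut-point. An illustrative split at 10 weeks, with planned durations spread over weeks 2 to 26, gives about 0.34 (constant) and 0.24 (shape 0.7).

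**5. After the fix.** With only patients event-free at the landmark and the clock restarted there, HRs are 1.00 and 1.02 for prophylaxis (week 10), and 0.99 and 1.01 for ART timing (week 8). False-positive rates are 2.5% to 7%, consistent with 5% given the number of replicates.

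**The case against.** The best reply is that the protocol never commits to a naive analysis. Landmark and time-updated Cox models are time-to-event methods, so a sound analysis fits the sentence in Section 8.1, and a separate SAP may set time zero and exposure handling. This stands in part: a reader might infer that the plan will produce these false effects, and the text does not go that far. It does not dispose of the point, because the groups as listed are the source of the bias. Prophylaxis versus none, taken literally, puts everyone who failed before prophylaxis was possible into the none group.

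The prophylaxis figure is also a worst case. The cost-effectiveness text in Section 3 compares prophylaxis with patients who stop fluconazole without it, which would exclude people failing while still on fluconazole or never started. That stands. It also shows that the protocol uses two different comparators.

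A reader might further infer that these subgroups determine the Year 2-5 interventions. Section 3 does not support that. It ties the interventions to barriers found in the cascade of care, and the four examples concern titre, training, result delivery and titre-based therapy. None rests on ART timing, fluconazole duration or prophylaxis.

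Nor is item (e), culture-positive meningitis, an instance of guaranteed survival time. It appears only in Section 3, names no comparator, and mostly describes how episodes are captured. Its difficulty is overlap with the endpoint. The risk-factor text in Section 3 is tentative and names no method, so it adds little.

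**Conclusion.** The point holds for four listed groups: ART at 2 weeks, ART at 4 weeks or later, duration of fluconazole, and secondary prophylaxis. Analysed as listed from CRAG+, they would tend to favour later or longer treatment with no true effect. The false HR is about 0.4 to 0.3 for prophylaxis, well beyond the 0.73 that mirrors the plan's detectable effect. It is about 0.74 to 0.5-0.6 for ART at 4 weeks or later versus same-day, which is at or beyond that mark. For ART at 2 weeks the bias is small under constant hazard (0.91) and larger only if failures cluster early (0.76).

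These values illustrate scale and do not predict results. The 70% survival and the 2 + 8 week schedule come from the protocol. The 50% uptake, the hazard shape, the reading of week 10 as the start of prophylaxis, the spread of ART starts and the clock from CRAG+ are assumptions.

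The fault does not extend to the whole subgroup programme. The overall 6-month rate, the titre contrast and its power table, and the other factors fixed by the time of the CRAG result are not affected. Pre-existing and same-day ART carry no guaranteed time themselves. The bias enters only when they are compared with the later-start groups.

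**What to change.** In Section 8.1:

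- State one time zero, for example the CRAG specimen date.
- Analyse ART start, fluconazole duration and secondary prophylaxis as time-updated exposures in the Cox model, or by landmark among patients event-free and in follow-up at the landmark.
- Make the ART-timing categories exhaustive. As listed they have no place for starts between the result and 2 weeks, between 2 and 4 weeks, or for patients not started by the landmark.
- Use one definition of the prophylaxis comparator in Section 8.1, in Section 3 item (f) and in the cost-effectiveness text of Section 3.
- Move culture-positive meningitis (Section 3 item e) from the comparison groups to the outcomes.

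The cost is some wording and a little more analysis. Section 5 already collects fluconazole dates, ART timing and the date last known alive. Landmarking drops early failures from these contrasts and loses some precision. Neither method removes confounding by indication, since the reasons for starting late or continuing longer are related to prognosis. The protocol should say so and present these contrasts as associations.

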No. Main groups of underlying causes of death (based on ICD-	Number	Percentage	
10)			
1 Certain infectious and parasitic diseases (A00-B99)*	98 817	21,8	
2 Neoplasms (C00-D48)	39 143	8,6	
3 Diseases of the blood and immune mechanism (D50-D89)	9 594	2,1	
4 Endocrine, nutritional and metabolic diseases (E00-E90)	29 642	6,5	
5 Mental and behavioural disorders (F00-F99)	1 996	0,4	
6 Diseases of the nervous system (G00-G99)	10 274	2,3	
7 Diseases of the eye and adnexa (H00-H59)	16	0,0	
8 Diseases of the ear and mastoid process (H60-H95)	54	0,0	
9 Diseases of the circulatory system (I00-I99)	78 258	17,3	
10 Diseases of the respiratory system (J00-J99)	45 381	10,0	
11 Diseases of the digestive system (K00-K93)	11 928	2,6	
12 Diseases of the skin and subcutaneous tissue (L00-L99)	793	0,2	
13 Diseases of the musculoskeletal system etc. (M00-M99)	1 619	0,4	
14 Diseases of the genitourinary system (N00-N99)	8 772	1,9	
15 Pregnancy, childbirth and puerperium (O00-O99)	1 027	0,2	
16 Certain conditions originating in the perinatal period (P00-P96)	9 363	2,1	
17 Congenital malformations (Q00-Q99)	2 138	0,5	
18 Symptoms and signs not elsewhere classified (R00-R99)	56 784	12,5	
19 External causes of morbidity and mortality (V01-Y98)	47 761	10,5	
Total 453 360 100			
* Including deaths due to MDR-TB and XDR-TB.			

The table below shows death distribution by causes:

Knowledge gaps in the implementation of CRAG screening and treatment interventions

- Retention-in care: In a pilot study in Soweto, important challenges to real-world implementation were identified, including high rates (48%) of loss-to-follow-up among CRAG+ patients (31). Here, linkage and retention-in-care was essential to the success of the CRAG screening program.
- Linkage to laboratory results: Poor linkage to laboratory (CD4 and CRAG testing) results was identified as a major operational barrier during an evaluation of the first phase of reflex CRAG screening at 200 health facilities in 4 South African health districts (approximately 20%).

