4.2 Subject Exclusion Criteria

• Age <18 years

Rationale for Criteria:

This project will generate an epidemiological dataset and will then explore the primary endpoint for pre-specified subgroups, along with operational challenges amongst specific subgroups.

STUDY EVALUATIONS 5

We will collect 3 types of data: patient-level, clinic-level, and laboratory-level.

Patient-level data

Chart review will occur approximately 3 times over a 6 month period, with the goal of capturing the patient-level information on CRAG+ persons. Timing of these chart reviews will be variable.

The chart abstractor will ensure that the subject has a positive CRAG result. If so, additional clinical information will be extracted from the chart (see below).

Informed consent will not be obtained for this study, as we are retrospectively collecting demographics and outcomes for CRAG+ and CRAG- patients in routine care. Please see Informed Consent section below.

Baseline demographic information will be obtained, including age, sex, date of birth, location, distance from clinic. Thereafter information about CRAG screening will be obtained. Namely, whether CRAG results were returned to the medical chart and how the healthcare provider acted on these results. If symptomatic, were they offered an LP? If asymptomatic were they prescribed fluconazole? What were the doses and dates of fluconazole therapy, and were there any side effects. Timing of initiation of ART and active treatment for TB will be obtained from the chart. Survival status, along with the date that the patient was last known to be alive will also be collected.

	ecieu
Evaluations	Monitoring Visit
CRAG+, titre	х
CD4 count	Х
Baseline demographic data	Х
If symptomatic, receipt of LP	х
If asymptomatic, receipt of fluconazole	х

Patient-level	data	to be	collected

Evaluations	Monitoring Visit
Completion of fluconazole	Х
Initiation of ART (timing)	Х
Concurrently on TB treatment	Х
Incidence of cryptococcal Meningitis	Х
6-month retention in care	х
6-month vital status	Х

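### The ART-timing subgroups mix whether results were known with elapsed time, so the same-day ART contrast can partly reflect result delivery rather than ART timing

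*Protocol*

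**What the plan says.** Protocol section 8.1 lists timing of ART initiation among its a priori subgroups, with four categories:

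- a group whose treatment was already in place before screening
- an early group, defined by information: "Initiated on ART before CD4/ CRAG results are known (same-day ART initiation in the context of universal HIV test-and-treat")
- a first later group, defined by elapsed time: "ART initiated at 2 weeks"
- a second later group, also defined by elapsed time: "ART initiated at >=4 weeks"

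Section 3, Subgroup Analyses (a), uses the same information-based wording for its early group. It sets that group against patients whose ART was "delayed until a minimum of 2 weeks of antifungal treatment completion".

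Neither section gives a day limit for the early group, or says to whom, or by when, a result must be known.

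Three other parts of the protocol bear on this:

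- Section 1.1, on knowledge gaps: "Poor linkage to laboratory (CD4 and CRAG testing) results was identified as a major operational barrier". A figure of approximately 20% follows, but its denominator is unclear.
- Section 1.1 also reports that 63% of CRAG-positive persons were treated with fluconazole in the first phase, that treated persons generally do better than untreated ones, and that 25%-30% of treated persons still develop meningitis or die.
- Section 5, patient-level data, lists what is abstracted about screening: "Namely, whether CRAG results were returned to the medical chart and how the healthcare provider acted on these results". CD4 count and the timing of ART initiation are abstracted too.

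**The concern.** Having a result known and starting ART on a given day are different things. A programme with poor result delivery will have patients for whom the two come apart. If a CRAG-positive result never reaches the provider, an ART start in week 1 or week 8 is equally a start before the result is known.

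Such patients are not a random sample. They would not be given fluconazole because of the result, and the protocol expects untreated patients to do worse. The error therefore leans towards apparent harm from early ART.

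Section 1.1 describes the effect of same-day ART on outcomes at programme level as unknown, and section 3 lists rapid or same-day ART as a candidate risk factor for treatment failure. The interventions for years 2-5 are to be chosen from the barriers seen in the earlier data. If missed results are read as an effect of ART timing, attention could move away from result delivery, which is one of the example interventions.

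**Working it through.** **No stated figure to reproduce.** The protocol gives no effect size or power for ART timing. The detectable hazard ratio of 1.37 in section 8.1 is for 300 high-titre against 900 low-titre patients. A two-proportion calculation at 80% power reproduces it closely (event-free proportion 0.612, HR 1.377). It is not a benchmark for this contrast.

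**Where patients fall, reading the section 8.1 categories literally (new starters)**

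| ART start | Result seen before the start | Result never seen |
|---|---|---|
| Same day as the CD4 draw | not applicable | before-known group |
| Day 5 | no group | before-known group only |
| 2 weeks | 2-week group | before-known **and** 2-week groups |
| Week 3 | no group | before-known group only |
| Week 5 | >=4-week group | before-known **and** >=4-week groups |

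The categories overlap and leave gaps. In section 3(a), a patient whose result was never seen is in effect shut out of the comparator, because entry needs at least 2 weeks of antifungal treatment.

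**Illustration of size.** All inputs are assumptions except that the 30% failure matches the 70% event-free control survival used in section 8.1 and the upper end of the 25%-30% in section 1.1.

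- True ART-timing effect: none
- q = 0.20, results never known, independent of timing
- s = 0.20, truly same-day starters
- a = 0.70, share of the others who start later
- Failure at 6 months: 0.30 if the result is known, 0.50 if never known
- HR = ln(1 - failure in early group) / ln(1 - failure in comparator)

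*Failure in each group*

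- True same-day starters: 0.8 × 0.30 + 0.2 × 0.50 = 0.34.
- Time-defined later starters, including missed results: the same mixture, 0.34.
- Section 3(a) comparator, with no missed results: 0.30.
- Literal before-known group. Its share is 0.20 + 0.80 × 0.20 × 0.70 = 0.312, of which 0.112/0.312 = 36% are not same-day starters. Failure is (0.20 × 0.34 + 0.112 × 0.50)/0.312 = 0.124/0.312 = 0.397.

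*Contrasts*

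| Early group | Comparator | Failure | Apparent HR |
|---|---|---|---|
| True same-day | 3(a) comparator | 34% vs 30% | ln 0.66 / ln 0.70 = 1.16 |
| Literal | Time groups with overlap | 39.7% vs 34% | ln 0.603 / ln 0.66 = 1.22 |
| Literal | Comparator with no missed results | 39.7% vs 30% | ln 0.603 / ln 0.70 = 1.42 |
| Same-day by date | Later by date | 34% vs 34% | 1.00 |

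**Range.** Let q run over 0.1-0.3, s over 0.2-0.5, a over 0.7-0.9, and failure if never known over 0.40-0.50. The same formulas give 1.04-1.25 for the first contrast, 1.02-1.27 for the second and 1.06-1.59 for the third. The low ends come from q = 0.1, s = 0.5, a = 0.7 and failure 0.40. The high ends come from q = 0.3, s = 0.2, a = 0.9 and failure 0.50.

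**The case against.** The strongest reply is that the text says who is meant. The bullet sits under timing of ART initiation and its bracket names same-day ART. Section 1.1 explains that many patients start on the day of HIV diagnosis, well before results are available. On that reading, known means available from the laboratory, and a week-8 starter does not belong in the group. The risk-factor objective in section 3 also anchors delayed ART to the CD4 draw and lists delayed fluconazole separately. A day window is something an analysis plan could supply.

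Much of this stands. Same-day starters are plainly intended, and limiting the group to them removes the literal misclassification. Two things remain. The protocol itself fixes the criterion, in the same words in two places, and a bracketed gloss is not a rule that several partners abstracting charts will apply alike. And the limiting reading does not repair section 3(a), where the comparator is still selected for a delivered and treated result.

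A reader might go further and infer that the plan will show harm from same-day ART where there is none, at a hazard ratio around 1.42 and above what section 8.1 calls detectable. The documents do not support that. The 1.42 needs the literal group set against a comparator with no missed results, yet the section 8.1 time groups do not exclude missed results. The 1.37 concerns titre. The failure rate after a missed result and all the mixing shares are assumed.

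**Conclusion.** The point holds as a definition problem in a named a priori subgroup; the overall primary estimate is not affected. The section 8.1 categories are neither mutually exclusive nor exhaustive. The section 3(a) contrast can partly measure result delivery, however its bracket is read.

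The direction, towards apparent harm from early ART, follows from the protocol's own statements on linkage and on outcome with treatment. The size does not. On the illustrative assumptions it is modest, at about 1.16 to 1.22 for the two contrasts that the text supports, and it is close to nil at the favourable end of the range. These figures rest on no true timing effect, on missed results being independent of timing, and on the assumed higher failure when a result is never seen.

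**What to change.** For analysis only, and with no bearing on how patients are managed, amend sections 8.1 and 3(a) as follows:

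- Define ART-timing groups by ART start date relative to CD4 draw date: pre-existing ART, same-day ART within a fixed window, then later intervals that join without gaps. Each ART starter falls in exactly one group.
- Define no group by whether results were known or by antifungal treatment completed.
- Keep return of the CRAG result as a separate factor. Report the timing contrast overall and among patients whose result was returned.

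In the illustration, both reports give a hazard ratio of 1.00 when timing has no effect (34% vs 34% overall, 30% vs 30% among those with a known result).

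The cost is wording: section 5 already collects ART timing, CD4 results and result return. The day window is arbitrary and should be fixed before the data are examined. Date-based grouping does not remove other confounding, nor the selection that arises because later starters must survive to their start date. The report should acknowledge both.

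### The a priori ART-timing groups in Section 8.1 have gaps and no time origin, so the ART-timing comparison leaves out patients, including those who die before starting ART

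*Protocol*

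**What the plan says.** The protocol describes ART timing for analysis in three places.

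- **Section 8.1.** Under "The a priori subgroups of interest are", the ART-timing item has four levels: "On pre-existing ART"; "Initiated on ART before CD4/ CRAG results are known"; a level for starts at 2 weeks; and "ART initiated at >=4 weeks". The section says subgroups will be compared on the primary endpoint with time-to-event methods. It does not say from which date the weeks are counted or how wide the 2-week level is.
- **Section 3, Subgroup Analyses, item (a).** Introduced by "For example, we will compare outcomes amongst CRAG+ persons who", this is a two-group contrast. One group started ART before the results were known. The other is "those who have ART delayed until a minimum of 2 weeks of antifungal treatment completion", which has no upper limit and is counted in antifungal treatment time.
- **Section 3, Secondary Objectives, risk factors for treatment failure.** Candidate risk factors include a rapid or same-day start, and a start more than 2 weeks after the blood draw for the CD4 count.

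Two other statements bear on this. Section 8 counts death from any cause as a failure of the primary endpoint. Section 5 collects the timing of ART initiation, the dates of fluconazole therapy and the date last known alive.

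**The concern.** Whether same-day ART affects outcomes in advanced HIV is one of the knowledge gaps named in Section 1.1, so this comparison should have clear groups. The 8.1 levels look like a full classification but do not cover the possible start times. The uncovered patients are not a random subset: they are defined by when, and whether, they reached ART. A patient who dies in the first weeks without starting has the event and yet belongs to no group. Membership is thus decided partly by the outcome being compared. With three definitions on different clocks, the same patient can also be classified differently depending on which section the analyst follows.

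**Working it through.** No sample size, power or event count is stated for the ART-timing subgroup, so there is no figure of the plan's own to reproduce. The check is to place every possible ART start in each definition.

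**Step 1. Map the start times.** Section 8.1 states no origin, so days from the result are assumed in its column.

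| ART start | Section 8.1 | Section 3, item (a) | Section 3, risk factors |
|---|---|---|---|
| Already on ART | pre-existing | not named | not named |
| Before the result | before result | early group | rapid or same-day |
| After the result, before 2 weeks | none | none, unless 2 weeks of antifungals are already complete | rapid, or delayed if more than 2 weeks from the draw |
| At 2 weeks | 2-week level | delayed | delayed if more than 2 weeks from the draw |
| Between 2 and 4 weeks | none if read literally | delayed | delayed |
| 4 weeks or later | last level | delayed | delayed |
| Never, including death before ART | none | none | not addressed |

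**Step 2. Count the uncovered start days in 8.1**, over days 1 to 27 after the result (27 possible days).

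- Literal reading, day 14 only: 27 − 1 = 26 days uncovered.
- Assumed window of 3 days either side (days 11 to 17, 7 days): 27 − 7 = 20 uncovered.
- Widest reading, 2-week level = days 14 to 27 (14 days): 27 − 14 = 13 uncovered, namely days 1 to 13.

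Never-starters are uncovered on all three readings. These are counts of days, not of patients. The protocol gives no distribution of start times, so they cannot be turned into a share of the cohort.

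**Step 3. Compare the clocks.** Take a patient whose fluconazole follows the result and who starts ART exactly 14 days after fluconazole began. The draw precedes the result, so this start is more than 14 days after the draw. The patient is at the 2-week boundary on the antifungal clock and already past 2 weeks on the blood-draw clock. The antifungal clock also has no starting point for an untreated patient. Section 1.1 reports that 63% of CRAG+ persons in the earlier phase received fluconazole, which leaves 100 − 63 = 37% without that origin if the same share applied here.

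**Step 4. Trace the outcome dependence.** To enter the last level, a patient must be alive at 4 weeks. Over a 6-month horizon of about 26 weeks, that is 4/26 = 15% of follow-up in which a member of that group cannot have died. A patient who meant to start later but died first is in no 8.1 group. Taken alone, this removes deaths from the later-start side. The other uncovered patients could move the comparison either way, so neither the net direction nor the size follows from the document.

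**The case against.** The strongest reply has four parts.

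1. The Section 3 list is illustrative and Section 8.1 holds the a priori list. Both share the before-results group, and if the 2-week level means 2 to under 4 weeks, 8.1 largely refines the open-ended delayed group. This stands. A reader might infer that the two sections are flatly incompatible, and the text does not show that. They are unreconciled, and even the refinement reading leaves days 1 to 13 and never-starters without a group.
2. Two of the gaps (starts after the result but before 2 weeks, and never-starters) are in Section 3(a) as well. Only the gap between 2 and 4 weeks is particular to 8.1. This also stands, and it is why both sections need the change.
3. Section 8.1 lists subgroups of interest and does not say that unlisted patients are excluded. The overall 6-month estimate still includes everyone, and the risk-factor objective would count a week-3 start from the draw as delayed. This is correct for the overall estimate. In the comparison among the listed groups, however, a patient with no group cannot contribute.
4. Windows, reference group and handling of several contrasts commonly belong in a statistical analysis plan, which is not at hand. Accepted for those items. The point here is that the protocol has itself fixed the categories, and they have gaps.

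**Conclusion.** The point holds for the ART-timing subgroup comparison, one of nine a priori subgroup items. On any reading the 8.1 categories omit starts between the result and 2 weeks and patients who never start; read literally, they also omit starts between 2 and 4 weeks. Section 3 defines ART timing differently in two further places. Applied as written, the comparison is partly selected on outcome. The gaps follow from the text; only the day counts assume the result date as origin.

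Two stronger inferences are not supported. A reader might take the overall 6-month cryptococcal meningitis-free survival estimate to be affected; it is not, because it does not use these groups. A reader might also attach a loss of power or an inflated false-positive rate to the four-level list. The protocol gives neither the share of patients who fall outside the categories nor a commitment to test every pair, so no such figure can be derived. The change should be made, but it concerns a secondary comparison.

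**What to change.** Replace the ART-timing wording in Section 8.1, Section 3 item (a) and the Section 3 risk-factor objective with one exhaustive, non-overlapping analysis classification, counted from one stated origin:

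- already on ART;
- started before the result was known;
- started after the result, in contiguous intervals (for example under 2 weeks, 2 to under 4 weeks, 4 weeks or later);
- not yet started.

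Exhaustive categories are not enough by themselves. A group defined as never started by 6 months would collect the early deaths, while each later-start group would still be conditioned on surviving to start. Making the Section 3(a) contrast the lead comparison would likewise keep the exclusion of patients who never start. The groups should therefore be compared in one of two ways:

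- **Time-varying exposure.** Each patient contributes time as not yet started until ART begins, and a death before ART counts in that state.
- **Landmark.** Patients are classified by ART status at a stated time and followed from there, with events before the landmark reported separately.

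The cost is mainly wording, because ART timing is already collected under Section 5. Some cells become smaller, and a landmark analysis needs separate handling of early events. The intervals are analysis categories only and imply nothing about when ART should be started in care.
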